Appendix D. Protocol Amendment: List of Changes

The summary of changes is listed in Section 1.1.

Specific Protocol Changes

Section 1.1 Synopsis

Subsection Objective:

First sentence previously read:

To assess the safety and effectiveness of the liquid formulation of palivizumab (Synagis[®]) administered as monthly intramuscular injections among preterm infants, infants with chronic lung disease (CLD) of prematurity and infants with hemodynamically significant congenital heart disease (CHD) in the Russian Federation and the Republic of Belarus.

Has been changed to read:

To collect further data on safety and effectiveness of the liquid formulation of palivizumab (Synagis[®]) administered as monthly intramuscular injections among preterm infants, infants with chronic lung disease (CLD) of prematurity and infants with hemodynamically significant congenital heart disease (CHD) in the Russian Federation and the Republic of Belarus.

Section 1.1 Synopsis

Subsection Statistical Methods:

Heading "Sample Size:"

First sentence previously read:

The objective of this study is to describe the effectiveness and safety of the liquid formulation of palivizumab in young children at high risk of severe RSV disease in the Russian Federation and the Republic of Belarus.

Has been changed to read:

The objective of this study is to collect further data on the effectiveness and safety of the liquid formulation of palivizumab in young children at high risk of severe RSV disease in the Russian Federation and the Republic of Belarus.

Section 3.0 Introduction

Tenth paragraph previously read:

This international, multicenter, open-label study is intended to examine the safety and effectiveness of palivizumab solution for injection in children at high risk of severe respiratory syncytial virus infection in the Russian Federation and the Republic of Belarus.

Has been changed to read:

This international, multicenter, open-label study is intended to collect further data on the safety and effectiveness of palivizumab solution for injection in children at high risk of severe respiratory syncytial virus infection in the Russian Federation and the Republic of Belarus.

Section 3.1 Differences Statement

Last sentence previously read:

This study will further describe the safety and effectiveness of palivizumab solution for injection in the Russian and Belarusian population.

Has been changed to read:

This study will collect further data on safety and effectiveness of palivizumab solution for injection in the Russian and Belarusian population.

Section 3.2 Benefits and Risks

First sentence previously read:

The present study is a prospective, multicenter, open-label, non-controlled study to describe safety and effectiveness of palivizumab solution for injection in the Russian and Belarusian population of preterm infants, infants with chronic lung disease (CLD) of prematurity and infants with hemodynamically significant congenital heart disease (CHD).

Has been changed to read:

The present study is a prospective, multicenter, open-label, non-controlled study to collect further data on safety and effectiveness of palivizumab solution for injection in the Russian and Belarusian population of preterm infants, infants with chronic lung disease (CLD) of prematurity and infants with hemodynamically significant congenital heart disease (CHD).

Section 4.0 Study Objective

Previously read:

The objective of this study is to describe the safety and effectiveness of palivizumab solution for injection administered as monthly intramuscular injections among preterm infants (≤ 35 wGA), infants with CLD of prematurity and infants with hemodynamically significant CHD in the Russian Federation and the Republic of Belarus.

Has been changed to read:

The objective of this study is to collect further data on safety and effectiveness of palivizumab solution for injection administered as monthly intramuscular injections among preterm infants (≤ 35 wGA), infants with CLD of prematurity and infants with hemodynamically significant CHD in the Russian Federation and the Republic of Belarus.

Section 5.6.1 Discussion of Study Design and Choice of Control Groups

Previously read:

This is a prospective, multicenter, open-label, non-comparative clinical study, designed to describe the safety and effectiveness of palivizumab solution for injection when administered as RSV prophylaxis to high-risk infants in the Russian Federation and the Republic of Belarus to meet regulatory requirements of the Russian Ministry of Health.

Has been changed to read:

This is a prospective, multicenter, open-label, non-comparative clinical study, designed to collect further data on safety and effectiveness of palivizumab solution for injection when administered as RSV prophylaxis to high-risk infants in the Russian Federation and the Republic of Belarus to meet regulatory requirements of the Russian Ministry of Health.

### **3.0 Introduction**

This analysis plan reflects Study Protocol M15-539 dated 21 January 2016, including Amendment 1 dated 25 May 2016. It takes into account the ICH Guidelines E3 and E9.

The SAP will provide details to further elaborate statistical methods as outlined in the protocol and will describe analysis conventions to guide the statistical programming work. The SAP will be signed off before the database lock.

All data will be verified and validated according to the latest version of the integrated data review plan (IDRP).

The analysis will be performed by AbbVie using SAS® in a UNIX environment, the release currently implemented at the time of analysis.

### **4.0 Study Objectives, Design and Procedures**

#### **4.1 Objectives**

The objectives of this study are to collect further data on safety and effectiveness of the liquid formulation of palivizumab (Synagis®) administered as monthly intramuscular injections among preterm infants, infants with chronic lung disease (CLD) of prematurity and infants with hemodynamically significant congenital heart disease (CHD) in the Russian Federation and the Republic of Belarus.

#### **4.2 Study Design**

This is a Phase 3b, prospective, multicenter, open-label, non-controlled study of immunoprophylaxis with the intramuscular (IM) administration of palivizumab for the prevention of RSV hospitalizations in infants at high risk. Approximately 50 infants will be enrolled in the study and will receive palivizumab solution for injection at 15 mg/kg by IM injection every 30 days for a minimum of 3 and a maximum of 5 injections given during anticipated periods of RSV risk in the community; the number of doses will depend on the time of enrollment during the RSV season. Prior to each injection of study

drug all enrolled subjects will undergo safety assessment. All subjects that received at least one injection of palivizumab will be followed by a telephone contact at 30 and 100 days after their last injection.

All cardiac/respiratory hospitalizations or deterioration in the cardiac/respiratory status in a hospitalized infant will be evaluated by testing nasopharyngeal specimens with a commercially available licensed RSV diagnostic test (RT-PCR) to determine if RSV contributed to the hospitalization or deterioration.

### **4.3 Sample Size**

No formal sample size calculation was performed for this descriptive study and the sample size is based primarily on practical considerations. It is anticipated that approximately 50 subjects will be enrolled. With a sample size of 50 subjects, the width of the 95% exact confidence interval in case of 0, 1, 2, 3 RSV hospitalizations (i.e., event rates of 0%, 2%, 4%, 6%) would be 7.1% (lower bound 0%; upper bound 7.1%), 10.6% (0.1%; 10.6%), 13.2% (0.5%; 13.7%), 15.3% (1.2%; 16.5%), respectively.

### **4.4 Interim Analysis**

No interim analysis will be done.

## **5.0 Analysis Populations**

### **5.1 Definition of Analysis Populations**

All analyses will be performed on the intent-to-treat (ITT) set, defined as all enrolled subjects who received at least one dose of study drug, unless otherwise indicated.

The safety analyses will be performed on the safety set which is identical to the ITT set.

### **5.2 Variables Used for Stratification of Randomization**

Not applicable.

## 6.0 Analysis Conventions

### Definition of Baseline

For any variable, the baseline value is defined as the last non-missing value on or before the date and time (if applicable) of first administration of study drug.

### Definition of Analysis Windows

The following visit windows will be used to assign visit numbers for analysis. If the assigned visit number results in more than one non-missing assessment in a given visit window, then the assessment performed closest to the nominal day will be used in analyses. When more than 1 day is of equal proximity to the nominal day, then the data collected after the nominal day will be used in analyses.

Visit windows depend on when a variable is measured during the study.

RxDAY is defined as the number of days between the day of the first dose of study drug and the day of the time point of interest.

$RxDAY = \text{date of visit} - \text{date of first study drug} + 1.$

RxDAYs are negative values when the time point of interest is prior to the first study drug dose day. RxDAYs are positive values when the time point of interest is on or after the first study drug dose day. The day of the first dose of study drug is defined as RxDAY 1, while the day prior to the first study drug dose is defined as RxDAY -1 (there is no RxDAY 0).

**Table 1. Visit Windows**

Scheduled Visit Day	Nominal RxDAY	First RxDAY	Last RxDAY
0	1		1
30	30	2	45
60	60	46	75
90	90	76	105
120	120	106	

Vital signs (blood pressure, respiration rate, heart rate, body temperature), body weight and body height values obtained more than 30 days after the last dose of study drug will not be included in the analyses.

Enrollment date is defined as date of first visit.

## **7.0 Demographics, Baseline Characteristics, Medical History, and Previous/Concomitant Medications**

Demographics, baseline characteristics, medical history and previous/concomitant medication will be assessed for the ITT set.

### **7.1 Demographic and Baseline Characteristics**

The following demographic and baseline characteristics will be summarized.

Continuous data will be summarized with the number of non-missing observations by mean, standard deviation, median, first and third quartile, minimum and maximum values.

Categorical data will be summarized using frequencies and percentages. The number of subjects with missing information will also be summarized; however, percentages will be calculated based on non-missing values.

Tables for subject demographics including body height and weight will also be stratified by sex.

### **Subject Demographics**

- Sex [male, female]
- Age [months] defined as the number of months from date of birth to date of first study drug, i.e., the integer of (age in days/30).
- Age categories [0 – 3, 4 – 6, 7 – 9, 10 – 12, 13 – 15, 16 – 18, 19 – 21, 22 – 24 months)
- Ethnicity [Hispanic or Latino, Not Hispanic or Latino]
- Race [White, Black or African American, Asian, American Indian or Alaska Native, Native Hawaiian or Other Pacific Islander, Multi Race; if Asian: Japanese, Chinese, Korean, Taiwanese, other]
- Body height [cm]
- Body weight [kg]
- Body weight categories [ $\leq 3.33$  kg,  $> 3.33$  to  $\leq 6.66$  kg, subtotal  $\leq 6.66$  kg,  $> 6.66$  to  $\leq 10.00$  kg,  $> 10.00$  to  $\leq 13.33$  kg, subtotal  $> 6.66$  to  $\leq 13.33$  kg,  $> 13.33$  kg]

### **Criteria of High Risk of Severe RSV Infection**

- Infant born  $< 35$  weeks gestational age AND  $\leq 6$  months of age at enrollment
- Infant  $\leq 24$  months of age at enrollment AND with a diagnosis of Bronchopulmonary Dysplasia (BPD)
- Infant  $\leq 24$  months of age at enrollment with Hemodynamically Significant Congenital Heart Disease (CHD)
- Any combinations of the above
- *For subjects with CHD:* Subject status [unoperated, partially corrected]
- *For subjects with CHD:* Type of CHD [Cyanotic, Acyanotic with pulmonary hypertension, Acyanotic with daily medication]

### **Subject's Medical History at Birth/RSV Hospitalization After Birth**

- Weeks gestational age (wGA) [weeks]
- Weeks gestational age categories [ $< 29$ ,  $29 - 32$ ,  $33 - 35$ ,  $> 35$  wGA]

- Birth weight [grams]
- Subject product of multifetal pregnancy [yes, no]
- Subject hospitalized for RSV after birth [yes, no]
- *If yes:* number of RSV hospitalizations (*categorical*)

### **Subject's Social History**

- Number of rooms in the home (*continuous, categorical*)
- Number of people in the home > 13 years old (*continuous, categorical*)
- Number of other children in the home  $\leq$  13 years old (*continuous, categorical*)
- subject attends day care [yes, no]
- other children ( $\leq$  13 years old) in the home attend daycare/school [yes, no]
- Number of furred pets inside the home (*continuous, categorical*)
- subject exposed to tobacco smoke in the home [yes, no]

### **Subject's Alimentary Diet**

- subject ever breastfed [yes, no]
- *if ever breastfed:* currently breastfed [yes, no]
- *if ever breastfed:* duration breastfed [months] (*continuous, categorical*)
- *if ever breastfed:* currently receiving non-human breast milk [yes, no]
- *if ever breastfed:* age when non-human breast milk was introduced [months] (*continuous, categorical*)
- *if ever breastfed:* currently receiving solid food [yes, no]
- *if ever breastfed:* age at first solid food intake [yes, no] (*continuous, categorical*)

### **Mother's Medical History**

- Number of pregnancies (*continuous, categorical*)
- Number of deliveries (*continuous, categorical*)
- Number of abortions (*continuous, categorical*)

- Number of miscarriages (*continuous, categorical*)
- subject's mother smoked while pregnant with the subject [yes, no]

### **Family History/Family History of Atopy and Immunodeficiency**

- Father's age at enrollment visit calculated as number of years between father's birth date (imputed as 01 JAN of the birth year) and enrollment date [years]
- Mother's age at enrollment visit calculated as number of years between mother's birth date (imputed as 01 JAN of the birth year) and enrollment date [years]
- Father's highest educational level [illiterate, school, high school, college, post graduate, unknown]
- Mother's highest educational level [illiterate, school, high school, college, post graduate, unknown]
- Family members with asthma [yes, no, unknown]
- Family members with allergic bronchitis [yes, no, unknown]
- Family members with allergic rhinitis/rhinosinusitis [yes, no, unknown]
- Family members with immunodeficiency [yes, no, unknown]

## **7.2 Medical History**

Medical history data will be summarized and presented using body systems and conditions/diagnoses as captured on the eCRF. The body systems will be presented in alphabetical order and the conditions/diagnoses will be presented in alphabetical order within each body system. The number and percentage of subjects with a particular condition/diagnosis will be summarized for each treatment group. Subjects reporting more than one condition/diagnosis within a body system will be counted only once for that body system.

## **7.3 Previous Treatment and Concomitant Medications**

Medication is coded in WHODrug.

Prior and concomitant medications will be summarized. A prior medication is defined as any medication taken prior to the first dose of study drug. A concomitant medication is defined as any medication that started prior to the first dose of study drug and continued to be taken after the first dose of study drug or any medication that started after the first dose of study drug, but not after the last dose of study drug. The number and percentage of subjects who had taken medications will be summarized by generic drug name for both prior and concomitant medications.

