5.2.3 Prior and Concomitant Therapy

Any medication or vaccine (including over-the-counter or prescription medicines, vitamins and/or herbal supplements) administered to the subject during 2 weeks prior to enrollment, at the time of enrollment, or received during the study until 100 days after the last study drug injection must be recorded in the primary documentation and the study case report form (CRF) along with the reason for use, date(s) of administration including start and end dates, and dosage information including dose and frequency.

The AbbVie Monitor should be contacted if there are any questions regarding prior or concomitant therapy(ies).

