5.2.3.2 Concomitant Therapy

The following medications are not allowed during the study unless medically required:

- Immunoglobulin products possibly containing RSV antibodies such as intravenous immunoglobulins (blood transfusions are permitted);
- Chronic immunosuppressive medication (topical calcineurin inhibitors, topical and inhaled corticosteroids as well as short-course [≤ 7 consecutive days] systemic steroids are permitted);
- Any investigational agents.

Any concomitant treatment administered from first dose up to 100 days after last study drug injection will be documented on the appropriate CRF.

Receipt of any of the above during the study must be immediately (within 1 working day) reported to the sponsor since they may affect RSV infection.

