A complete physical examination will be performed at visits specified in [Appendix C](#). A symptom-directed physical examination may be performed at any other visit, when necessary. Any significant physical examination findings after the first dose of study drug will be recorded as adverse events.

Body Length/Height

The Investigator/designee will measure body length/height as indicated in the visit schedule in [Appendix C](#) and record the information in the subject's source and the eCRF.

Vital Signs

At each of the on-site study visits, vital signs will be taken prior to the study drug injection and repeated at 30 minutes after the study drug injection.

Assessment of RSV Hospitalizations

At every subject visit during treatment up to the follow up phone contact 1, the investigator/designee will follow-up on any subject hospitalizations for respiratory and/or cardiac reasons or any onset of new respiratory and/or cardiac symptoms in an already hospitalized subject with the parent(s)/legal guardian(s). The investigator/designee will follow the documentation requirements for RSV hospitalizations and take a note in the subject's source.

In case of cardiac/respiratory hospitalization, an RSV test might be taken by the investigator or designee if the test can be conducted within 48 hours of the hospitalization.

Follow-Up Phone Contact 1

The contact will be performed via telephone. The contact date is calculated as the date of the last prophylaxis visit (LPV) +30 Days (+5 day window is allowed). This telephone

contact will also be performed in all subjects discontinued from the study (unless the reason for discontinuation is withdrawal of consent).

The following procedures will be performed during the telephone call:

1. Record all adverse events (serious and nonserious) in source documents and on the appropriate CRF. Report SAE(s) within 24 hours of becoming aware of the SAE(s).
2. Record all concomitant medications.
3. Collect information about hospitalizations, if applicable.

Follow-Up Phone Contact 2

The contact will be performed via telephone. The contact date is calculated as the date of the last prophylaxis visit (LPV) +100 Days (+5 day window is allowed). This telephone contact will also be performed in all subjects discontinued from the study (unless the reason for discontinuation is withdrawal of consent).

The following procedures will be performed during the telephone call:

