1. Record all adverse events (serious and nonserious) in source documents and on the appropriate CRF. Report SAE(s) within 24 hours of becoming aware of the SAE(s).

RSV Diagnostic Test

In case of a respiratory/cardiac hospitalization or prolongation of existing hospitalization associated with respiratory/cardiac symptoms (Section 5.3.2.1), the investigator or designee will obtain a respiratory secretion specimen by nasopharyngeal swab, nasopharyngeal lavage or aspiration for RSV detection. Tracheal secretions may be obtained in cases when a child is intubated. The specimen will be collected as soon as possible, within 48 hours of a respiratory/cardiac hospitalization or new

respiratory/cardiac symptoms in a hospitalized infant. Respiratory secretions in all cases of a respiratory/cardiac hospitalization or prolongation of existing hospitalization associated with respiratory/cardiac symptoms will be collected using nasopharyngeal lavage or aspiration technique (see below for details) as described and tested in a central laboratory for RSV using a validated real-time RT-PCR RSV diagnostic test.

In the event of acute respiratory/cardiac hospitalization at a hospital other than the study site, parent(s)/legal guardian(s) are requested to inform the study site immediately. The Investigator or designee must make arrangements to collect a respiratory secretion specimen for RSV testing as soon as possible, but no later than 48 hours following the admittance of the subject to the non-enrolling hospital. Permission will be sought in the consent form for examination of medical records from all such hospitalizations.

The parent(s)/legal guardian(s) will be instructed that the study site will be the preferred place to obtain a respiratory secretion specimen for RSV detection in the case of hospitalization.

Collection of Nasopharyngeal Specimen for RSV Testing

Specimen collection for RSV diagnostic testing may include either of the following techniques. The goal is to obtain a specimen containing epithelial cells and not simply exudate from the nares:

- Nasopharyngeal Swab Method
- Nasopharyngeal Wash: Syringe Method
- Nasopharyngeal Wash: Bulb Method
- Vacuum-assisted Nasopharyngeal Aspirate Method

Follow the instructions outlined in the central lab manual to obtain a specimen using the site preferred method.

Central Laboratory

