8.1.2 Demographics, Other Baseline Characteristics, and Risk Factors

Data will be summarized descriptively. For continuous variables, the mean, standard deviation, median, minimum and maximum values will be calculated. For categorical variables, the number and percentage of subjects in each category within an assessment will be calculated for non-missing data.

Other medications used prior to study drug initiation and continued during the study or initiated during the study will be summarized with frequencies and percentages.

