13.0 Completion of the Study

The investigator will conduct the study in compliance with the protocol and complete the study within the timeframe specified in the contract between the investigator and AbbVie.

Continuation of this study beyond this date must be mutually agreed upon in writing by both the investigator and AbbVie. The investigator will provide a final report to the IEC/IRB following conclusion of the study, and will forward a copy of this report to AbbVie or their representative.

The investigator must retain any records related to the study according to local requirements. If the investigator is not able to retain the records, he/she must notify AbbVie to arrange alternative archiving options.

AbbVie will select the signatory investigator from the investigators who participate in the study. Selection criteria for this investigator will include level of participation as well as significant knowledge of the clinical research, investigational drug and study protocol. The signatory investigator for the study will review and sign the final study report in accordance with the European Agency for the Evaluation of Medicinal Products (EMA) Guidance on Investigator's Signature for Study Reports.

The end-of-study is defined as the date of the last subject's follow-up contact, which is defined as 100 days following the final injection of palivizumab.

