Appendix C. Study Activities

Activity	Visit 1 Enrollment	Visit 2	Visit 3	Visit 4 ^a	Visit 5 ^b /ET	Follow-Up Contact 1 ^c	Follow-Up Contact 2 ^c
Timelines and Allowance Window^d	Day 0 Baseline	Day 30 (-5 Days)	Day 60 (±5 Days)	Day 90 (±5 Days)	Day 120 (±5 Days)	Last Prophylaxis Visit + 30 Days (+5 Days)	Last Prophylaxis Visit + 100 Days (+5 Days)
Informed Consent	X						
Provide subject card	X						
Medical and Birth History	X						
Prior ^e /Concomitant Medication	X	X	X	X	X	X	X
In-/Exclusion Criteria	X						
Assignment of Subject Number	X						
Demographics and Social History	X						
Physical Examination & Weight	X	X	X	X	X		
Body Length/Height	X						
Vital Signs ^f (HR, BP, RR, T°C)	X	X	X	X	X		
Monitor Adverse Events ^g	X ^g	X	X	X	X	X	X
Study Drug administration ^h	X ^h	X	X	X	X		
RSV Diagnostic Test ⁱ							
Assessment of RSV-Hospitalizations		X	X	X	X	X	X

ET = Early Termination

- a. Only applicable to subjects enrolled during November 2016 through December 2016.
- b. Only applicable to subjects enrolled during November 2016.

- c. Telephone contact by Investigator/designee.
- d. Allowance window is given in parentheses.
- e. Will be collected for medications given 2 weeks prior to enrollment.
- f. Vital signs to be measured prior to and 30 minutes after administration of study drug.
- g. SAEs to be registered from the time the study informed consent is signed.
- h. Only applicable to subjects fulfilling Inclusion/Exclusion Criteria.
- i. In case of a cardiac/respiratory hospitalization or deterioration in cardiac/respiratory status in a hospitalized infant, an RSV diagnostic test will be done as soon as possible, but not later than 48 hours of hospitalization.

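### SAP 7.3 keeps medications first started after the last injection out of both planned medication tables, although the protocol plans to summarize medications begun during the study

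*SAP*

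**What the plan says.** SAP 7.3 tabulates prior and concomitant medications, counting subjects by generic drug name. Prior means taken before the first dose. Concomitant has two limbs: begun before the first dose and carried on past it, or "any medication that started after the first dose of study drug, but not after the last dose of study drug".

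Protocol 8.1.2 describes the planned analysis. It covers medications begun before study drug and continued, "or initiated during the study will be summarized with frequencies and percentages". It gives no end date.

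Other protocol sections set the period:
- Section 5.2.3 covers medication "received during the study until 100 days after the last study drug injection must be recorded".
- Section 5.2.3.2 states: "Any concomitant treatment administered from first dose up to 100 days after last study drug injection will be documented on the appropriate CRF".
- Section 13.0 ends the study at the last subject's follow-up contact, "which is defined as 100 days following the final injection of palivizumab".

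The follow-up calls differ. In Section 5.3.1.1 the list for Contact 1 (30 days after the last prophylaxis visit) includes "Record all concomitant medications". The list for Contact 2 (100 days after that visit) has a single item: "Record all adverse events (serious and nonserious) in source documents and on the appropriate CRF", together with prompt reporting of serious events. Appendix C nevertheless marks prior/concomitant medication at both contacts.

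**The concern.** The SAP stops counting new medications at the last injection, while the protocol keeps collecting them and describes a summary without that cut-off. The SAP narrows a planned summary and does not say so.

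The cut-off also does not fit the SAP's other windows. Treatment-emergent adverse events are reported to 30 and to 100 days after the last dose (SAP 11.2.1). Exposure is counted to 100 days after the last injection (SAP 9.0). The primary endpoint runs to 30 days after the last dose (SAP 10.2). For a product given every 30 days, the medication definition leaves out the whole interval after the final injection.

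The protocol synopsis gives the purpose of the medication data as support for the safety assessment. Take a drug first given on day 10 after the last injection to treat an adverse event. The event is tabulated and the drug is recorded at Contact 1, but the drug appears in no planned medication summary.

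**Working it through.** The plan states no figure on this point, so there is none to reproduce. The check has four steps.

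**1. Classify a drug whose first use begins after the last dose.**
- Prior: no, because it was not taken before the first dose.
- Concomitant, first limb: no, because it did not start before the first dose.
- Concomitant, second limb: no, because it started after the last dose.

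It enters neither table.

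**2. Look for another SAP output that would show it.** SAP 7.3 names only the two tables. SAP 8.0 has a yes/no deviation item on excluded treatment during palivizumab treatment, which does not tabulate medications. No other SAP section plans a medication table or listing.

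**3. Establish which medications still count.** The tables count subjects by generic name.
- A drug ongoing at the last dose is counted.
- A drug used earlier on study under the same generic name is counted.
- A generic taken and stopped before the first dose, then restarted after the last dose, appears as prior. Its later use is missing from the concomitant table.

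**4. Size the gap as a share of time.** Protocol 5.5 and Table 1 put the on-schedule last dose at Day 120, 90 or 60 for 5, 4 or 3 doses. The primary window ends 30 days later. The secure share is 30 / (day of last dose + 30).

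| Case | Day of last dose | Share of primary window after it |
|---|---|---|
| 5 doses | 120 | 30/150 = 20.0% |
| 4 doses | 90 | 30/120 = 25.0% |
| 3 doses | 60 | 30/90 = 33.3% |
| Extra post-bypass dose at Day 150, if last | 150 | 30/180 = 16.7% |

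Moving the scheduled last dose 5 days late or early gives:
- 5 doses: 30/155 = 19.4% to 30/145 = 20.7%
- 4 doses: 30/125 = 24.0% to 30/115 = 26.1%
- 3 doses: 30/95 = 31.6% to 30/85 = 35.3%

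Early discontinuation raises the share. In a subject who receives one dose only, the whole window lies after the last dose (30/30).

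**The case against.** The strongest reply is that the conflict is inferred. Protocol 8.1.2 is the only protocol sentence about analysing medications, and it sets no end date. The 100-day limits in 5.2.3 and 5.2.3.2 govern recording, not tabulation. The SAP says that it elaborates the protocol's methods, and restricting concomitant use to the dosing period can be read as doing that. The data remain on the CRF, so reporting is lost and not information. The products most likely to affect RSV infection are restricted during the study, and under 5.2.3.2 their receipt must reach the sponsor within one working day whatever the SAP tabulates.

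Much of this stands, and it keeps the point minor. It does not remove the gap. A study that runs to 100 days after the final injection includes drugs begun in those days, so the plain sense of 8.1.2 covers them. The SAP neither reports them elsewhere nor says that it leaves them out.

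Two stronger readings are tempting, and the documents support neither.
- A reader might infer that about half of the medication data are lost, because the 100 days after the last dose are 100/220 = 45%, 100/190 = 53% or 100/160 = 63% of follow-up for 5, 4 or 3 doses. These are calendar shares, not shares of medications or subjects. Seventy of the 100 days fall after Contact 1, where the protocol is inconsistent about collection. The figures also ignore the extra post-bypass dose and early discontinuation.
- A reader might infer that the effectiveness or adverse event results are at risk. Neither analysis uses the SAP 7.3 definition.

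**Conclusion.** The gap is real and minor. Under SAP 7.3 a medication first started after the last injection reaches neither planned medication table, while Protocol 8.1.2, read with 5.2.3, 5.2.3.2 and 13.0, plans to summarize it.

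The secure extent is the 30 days to Contact 1: 20%, 25% or 33% of the primary window for 5, 4 or 3 doses, or about 17% if an extra dose at Day 150 were the last. The first three figures assume on-schedule dosing, no extra dose and no early discontinuation. Days 31 to 100 belong to the gap by definition, but how complete those data will be is uncertain until the Contact 2 instructions agree with the rest of the protocol. The consequence is confined to one descriptive safety-support table.

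**What to change.** In SAP 7.3, add a category for medications started after the last dose and up to 100 days after it. Report it by generic name in a separate column or a listing, apart from concomitant use during the dosing period. Classify each recorded course by its own start date, so that a drug taken only before the first dose and later restarted is shown there too. This brings the summary into line with Protocol 8.1.2 without mixing on-treatment and post-treatment use.

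Add a note that data for days 31 to 100 may be less complete. Reconcile the Contact 2 procedure list in Section 5.3.1.1 with 5.2.3, 5.2.3.2 and Appendix C on whether medications are recorded at that call.

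The cost is one added definition and one column or listing, with possibly incomplete late data as the only downside. The 30 days to Contact 1 need no new data collection. Timing also allowed it. The SAP is dated 30 January 2017. The earliest last dose for a subject completing the planned doses within the visit windows is 24 February 2017 (1 November 2016 + 115 days, or 1 December 2016 + 85 days), and that subject's Contact 2 falls no earlier than 4 June 2017 (+ 100 days). For these subjects the change could precede the calls.
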